3.6 Photography

Subjects at prospectively selected sites in the US will be asked to have optional photographs taken of their genitals (Study-G) or scalp (Study-S) to document disease response during the study. Photographs will be taken prior to study drug administration. Subjects must voluntarily provide consent, approved by an IRB/IEC, after the nature of the photographs has been explained and the subject has had an opportunity to ask questions. Subjects who agree to photographs are consenting to photographs at visits specified in Section 2.1.

Training and detailed instructions will be provided by the vendor selected to coordinate the photography portion of the study.

3.7 12-Lead Electrocardiogram

Resting 12-lead ECGs will be obtained singly as specified in Section 2.1.

The ECG acquired prior to dosing will serve as the baseline measurements for clinical assessment.

When an ECG is scheduled at the same time as a blood collection, the ECG will be obtained prior to the blood collection. ECGs occurring near meals will take place prior to meals.

ECGs will be acquired after the subject has been in the supine position for at least 5 minutes. Subjects will be instructed to remain completely stationary (no talking, laughing, deep breathing, sleeping, or swallowing) for approximately 10 seconds during the ECG recording. While ECGs are being acquired, subjects and staff are prohibited from having devices (e.g., cellular telephones, fans, heaters, etc.) that emit electrical interference in the room.

For subjects with a normal ECG taken within 90 days of Screening, a repeat ECG at Screening will not be required, provided all protocol-required documentation is available and nothing has changed in the subject's health status since the time of the test that warrants a repeat test.

ECG Safety Review

Each ECG will be evaluated by an appropriately trained physician (preferably a cardiologist) at the study site (the "local reader"). The local reading of the ECG will be used by the investigator for subject safety assessments, including adverse event determination and management, and decision on whether a subject is eligible for study participation.

The local reader will sign and date all the ECGs collected in this study and provide a global interpretation for each ECG using the following categories:

- Normal ECG

- Abnormal ECG – Not clinically significant (NCS)
- Abnormal ECG – Clinically significant (CS)
- Unable to evaluate

Clinically significant ECG findings noted at screening will be captured in Medical History.

All local reader evaluations of ECGs will be entered into the source documents. If the global interpretation is Abnormal (NCS or CS), the local reader will provide further information (e.g., sinus bradycardia, arrhythmia). The QT interval corrected for heart rate using QTcF will be calculated and documented for all ECGs.

All ECG source documentation will be retained at the study site. The automatic cardiograph reading (i.e., cardiograph-generated measurements and interpretations) will not be collected for analysis.

3.8 Height and Weight

Height will be measured at screening only. Body weight will be measured at scheduled visits as specified in Section 2.1. The subject will wear lightweight clothing and no shoes during weighing.

3.9 Vital Signs

Vital sign determinations of systolic and diastolic blood pressure, pulse rate, respiratory rate, and body temperature will be obtained at visits as specified in Section 2.1. Blood pressure and pulse rate should be measured after the subject has been sitting for at least 3 minutes.

Measurements should be assessed consistently throughout the study. Vital signs measurements determined prior to dosing on Baseline/Day 1 or specify timing will serve as baseline.

3.10 Physical Examination

A complete physical examination, including height (at Screening only) and weight, will be performed at the designated study visits as specified in Section 2.1. The physical examination performed at Baseline/Day 1 will serve as the baseline physical examination for the entire study. Any significant physical examination findings after the first dose will be recorded as adverse events, while any finding prior to the first dose will be recorded as medical history. All findings, whether related to an AE or part of a subject's medical history, will be captured on the appropriate eCRF page.

At any time, a symptom-directed physical examination can be performed as deemed necessary by the investigator.

3.11 Dispense Study Drug

Study drug will be administered to subjects beginning at Baseline/Day 1 and as specified in Section 2.1. All doses of risankizumab and placebo will be administered by designated and qualified study site

personnel under the direction of the investigator. Date and exact time (to the nearest minute) of study drug administration will be recorded on eCRFs. The first dose of study drug will be administered after all other Baseline procedures are completed. Study drug administration instruction for risankizumab PFS will be provided to the site.

Monitoring for Hypersensitivity Reactions

Therapeutic protein products, such as biologics, may elicit a range of acute effects, from symptomatic discomfort to sudden, fatal reactions and may encompass a wide range of clinical events, including anaphylaxis and other events that may not be directly related to antibody (Ab) responses, such as cytokine release syndrome.

Subjects should be closely monitored at the site for signs and symptoms of hypersensitivity reactions, including allergic reactions and anaphylaxis, for approximately 1 hour after all PFS dosing of study drug have been administered at each dosing visit. A medical person qualified in the treatment of acute hypersensitivity reactions must be present during the injections.

All appropriate medical support measures (e.g., antihistamines, steroids, epinephrine, oxygen) for the treatment of suspected hypersensitivity reactions should be available for immediate use in the event that a suspected hypersensitivity reaction occurs. Subjects who manifest any new signs or symptoms during the injection should be monitored for appropriate resolution prior to leaving the site. Subjects are encouraged to report any symptoms related to a possible injection-related reaction or local injection site reaction or late phase reactions to the site any time during the study. A patient information card listing the symptoms of these reactions will be provided to the participants.

Subjects will be monitored throughout the study for signs and symptoms suggestive of hypersensitivity reactions, including allergic reactions and anaphylaxis. In the event of a suspected anaphylactic/systemic hypersensitivity reaction, in addition to the standard AE eCRF, the supplemental Hypersensitivity Reaction Signs and Symptoms eCRF should also be completed by the site. The clinical criterion for diagnosing anaphylaxis is provided in Section 9.1 for reference; symptoms of anaphylactic reactions usually occur within minutes to hours after exposure to an allergen. These are guidelines that are used to help diagnose anaphylaxis. The investigator is encouraged to report any suspected reactions.

In the event of a suspected anaphylactic reaction, blood and serum samples should also be collected as described in Section 3.12.

3.12 Clinical Laboratory Tests

The blood samples for serum chemistry tests will be collected following a minimum 8-hour fast for the Baseline/Day 1 visit (glucose, total cholesterol, LDL-cholesterol, HDL-cholesterol, and triglycerides). If a subject is not able to fast at that visit, due to unforeseen circumstances, the non-fasting status will be recorded in study source documentation and lab requisition. Blood samples at other visits can be drawn without prior fast. The Baseline laboratory test results for clinical assessment for a particular test will be defined as the last measurement prior to the initial dose of study drug.

Blood draws should be performed after all questionnaires, clinical assessments, and vital sign determinations are obtained. Unscheduled clinical labs may be obtained at any time during the study if deemed appropriate per investigator's discretion.

A certified laboratory will be utilized to process and provide results for the clinical laboratory tests. Laboratory reference ranges will be obtained prior to the initiation of the study.

Instructions regarding the collection, processing, and shipping of these samples will be provided by the central laboratory.

If a laboratory test value is outside the reference range and the investigator considers the laboratory result to be clinically significant, the investigator will:

- repeat the test to verify the out-of-range value;
- follow the out-of-range value to a satisfactory clinical resolution; or
- discontinue the subject from the study or require the subject to receive treatment; in this case, the laboratory result will be recorded as an adverse event.

Clinical Laboratory Tests		
Hematology	Clinical Chemistry	Other Tests
Hematocrit Hemoglobin MCV RBC count/Erythrocytes WBC count/Leukocytes Platelet count/Thrombocytes Diff. Automatic (absolute count): Neutrophils Eosinophils Basophils Monocytes Lymphocytes Manual Differential (ONLY IF Automated Differential is abnormal): Neutrophils, bands (Stabs) Neutrophils, polymorphonuclear Eosinophils Basophils Monocytes Lymphocytes Coagulation: PT/INR ^a	Enzymes ALT AST AP GGT CK Only if CK is elevated: Troponin (point-of-care) OR Troponin (central lab) Electrolytes Sodium Potassium Chloride Bicarbonate Calcium Phosphorus Substrates Glucose BUN/Urea Creatinine with eGFR (CKD-EPI) Bilirubin total Bilirubin direct (if total is elevated) Bilirubin indirect (if total is elevated) Albumin hsCRP Cholesterol, total ^b LDL-C ^b HDL-C ^b Triglycerides ^b FSH ^c	Dipstick Urinalysis Urine nitrite Urine protein Urine glucose Urine ketone Urobilinogen Urine bilirubin Urine RBC/erythrocytes Urine WBC/leukocytes Urine pH Urine creatinine Urine Sediment (microscopic examination, ONLY IF urine analysis abnormal): Urine UACR
ADDITIONAL TESTING	INFECTION SCREENING^d	PREGNANCY TESTING^e
N/A	HBs Ag (qualitative) HBs Ab (qualitative) Anti-HBc total (qualitative) HBV DNA (quantitative) Anti-HCV (qualitative) HCV RNA (quantitative) HIV-1 and HIV-2 Ab (qualitative) QuantiFERON [®] -TB (or IGRA equivalent) and/or PPD	Urine pregnancy test (local) ^f Serum pregnancy test ^g ANAPHYLAXIS TESTING^h Serum risankizumab concentration ADA NAb Tryptase Histamine

- INR test only performed if ALT or AST > 3 × ULN (upper limit of normal).
- Performed at Baseline/Day 1 visit (following a minimum 8-hour fast).
- FSH testing is to be done at Screening in all women aged ≤ 55 years with no menses for 12 or more months without an alternative medical cause.

- d. Performed only at Screening. Per regional requirements: for subjects with HBs Ab (+) and/or HBc Ab (+) at Screening, the HBV-DNA PCR test should be performed again as noted in the Operations Manual, Section 3.12. Retesting is not necessary for subjects that have a history of HBV vaccine and are HBs Ab (+).
- e. Pregnancy testing is not required for female subjects of non-childbearing potential (defined in protocol Section 5.2).
- f. Urine pregnancy test will be performed at every dosing visit and must be conducted prior to study drug dosing. Negative urine pregnancy test results must be confirmed prior to study drug dosing.
- g. Serum pregnancy test is conducted at Screening and at other visits only if urine pregnancy test is positive. Negative serum pregnancy test results must be confirmed prior to study drug dosing.
- h. Only performed in case of a suspected anaphylactic reaction. Refer to anaphylaxis testing Section 9.1 below.

Urinalysis

Dipstick urinalysis will be completed by the central laboratory at all required visits. Specified abnormal macroscopic urinalyses defined as leukocytes, nitrite, protein, ketones, or blood greater than negative, or glucose greater than normal will be followed up with a microscopic analysis at the central laboratory.

Pregnancy Tests (Serum and Urine)

Pregnancy testing should not be performed for postmenopausal women. Determination of postmenopausal status will be made during the Screening Period based on the subject's history and confirmed by FSH, if appropriate.

A pregnant or breastfeeding female will not be eligible for participation or continuation in this study.

Pregnant subjects must discontinue from study drug treatment. Refer to Section 5.5 of the protocol for additional details.

Serum Pregnancy Test

A serum pregnancy test will be performed for all female subjects of childbearing potential (defined in the protocol) at Screening. The serum pregnancy test will be sent to and performed by the central laboratory. If the serum pregnancy test is positive, the subject is considered a screen failure. If the serum pregnancy test is borderline, study drug should be held and the test should be repeated ≥ 3 days later to determine eligibility.

If the repeat serum pregnancy test is:

- Positive, the subject is considered a screen failure;
- Negative, the subject can be enrolled into the trial;
- Still borderline ≥ 3 days later: If no clinical suspicion of pregnancy and there are other pathological causes of borderline results, the borderline results will be considered documentation of continued lack of a positive result and the subject can be enrolled into the study.

Urine Pregnancy Test

A urine pregnancy test will be performed for all females of childbearing potential at the Baseline Visit prior to the first dose of study drug. Additional urine pregnancy tests for female subjects of childbearing

potential will be performed at visits indicated in Section 2.1. More frequent pregnancy tests will be performed throughout the study if required per local/country requirements.

If the urine pregnancy test (which is performed at the site) is negative, dosing may begin or continue. If the urine pregnancy test is positive, dosing should be withheld, and a serum pregnancy test performed. Pregnant subjects must discontinue from the study.

Follicle-Stimulating Hormone

Follicle-stimulating hormone (FSH) should be tested at Screening if the female subject is ≤ 55 years of age AND has had no menses for ≥ 12 months AND has no history of permanent surgical sterilization.

Hepatitis B and C Testing

[figure not shown]
All subjects will be tested for the presence of the HBV and HCV at Screening (Figure 1). Subjects with HBs Ag positive [+] or detected sensitivity on the HBV-DNA PCR qualitative test) or hepatitis C (HCV RNA detectable in any subject with anti-HCV antibodies) will be excluded. Subjects who have been vaccinated against hepatitis B and are HBs Ab positive may be enrolled. If HBs Ag is negative but HbC Ab total is positive, HBV DNA will be quantified. If HBV DNA level is undetectable at Screening, the subject can participate in this trial.

Where mandated by local requirements, subjects with HBs Ab+ and/or HbC Ab+ and negative HBV DNA at screening should have HBV DNA PCR testing performed approximately every 12 weeks (q12w). HBV DNA PCR testing q12w is not necessary when the subject has a history of HBV vaccine and is HBs Ab+ and HbC Ab-.

Per regional requirements: for subjects with HBs Ab (+) and/or HbC Ab (+) at Screening, the HBV DNA PCR test should be performed as outlined in the Section 2.1. In cases where the recurrence of HBV-DNA is observed, the subject should be discontinued from the study drug. Retesting is not necessary for subjects that have a history of HBV vaccine and are HBs Ab (+).

If HCV antibodies are positive, HCV RNA will be quantified. If HCV RNA level is undetectable at Screening, the subject can participate in this trial.

Figure 1. Interpretation and Management of HBV Serologic Test Results

* A positive test result for HBs Ab is expected for subjects who have had a HBV vaccination. For subjects without a history of HBV vaccination (and where mandated by local requirements), a positive result for HBs Ab requires HBV DNA PCR testing.

HIV Testing

HIV testing will be performed at Screening. The investigator must discuss any local reporting requirements to local health agencies with the subject. The site will report confirmed positive results to their health agency per local regulations, if necessary. If a subject has a confirmed positive result, the investigator must discuss with the subject the potential implications to the subject's health and subject should receive or be referred for clinical care promptly. A subject will not be eligible for study participation if test results indicate a positive HIV infection. In case a screened subject has a confirmed positive HIV Ab test, Eligibility Criterion 13 should be selected in eCRF for documentation of screening failure.

Tuberculosis Screening

All subjects will be tested for TB by either the QuantiFERON-TB Gold Test (or IGRA equivalent) or a TB Skin Test (PPD) at the Screening visit and annually, or as specified in the study activity table.

At Screening and annually, or as specified in the study activity table, all subjects will be assessed for evidence of TB and TB risk factors. Subjects who have had a TB test performed within 90 days of the Screening Visit will not need to have the test repeated, provided all of the protocol required documentation is available at the site, and no new TB risk factors have been identified.

The QuantiFERON®-TB Gold test (or IGRA equivalent) will be supplied and analyzed by the central laboratory. (QuantiFERON-TB test is preferred over TB Skin Test.) Details on the collection, shipment of samples and reporting of results by the central laboratory are provided to investigators in the laboratory manual.

- If the **QuantiFERON-TB Gold Test (or IGRA equivalent) is NOT possible** or if both the QuantiFERON-TB Gold Test [or IGRA equivalent] and the PPD Skin Test are required per local guidelines, the PPD Skin Test will be performed according to standard clinical practice.

- The PPD Skin Test should be read by a licensed healthcare professional between 48 and 72 hours after administration. A subject who does not return within 72 hours will need to be rescheduled for another skin test.
- The reaction will be measured in millimeters (mm) of induration and induration ≥ 5 mm is considered a positive reaction. The absence of induration will be recorded as "0 mm," not "negative."
- If subject had a positive QuantiFERON-TB Gold (or IGRA equivalent) or PPD test at Screening, the test should not be repeated. Subjects who have had an ulcerating reaction to the TB Skin Test in the past should not be re-exposed and should not be tested by a PPD skin test.
- If the **TB screening test** (either PPD or the QuantiFERON-TB Gold test [or IGRA equivalent]) is **positive**, or if there is a **repeat indeterminate** QuantiFERON-TB Gold test (or IGRA equivalent) upon retesting, subjects may participate (or continue participation) in the study if **further work-up** (according to local practice/guidelines) establishes conclusively that the subject has **NO** evidence of active TB. If presence of **latent TB** is established, subjects should be treated (per local guidelines or by investigator judgement) with TB prophylaxis prior to receiving risankizumab or adalimumab and should be carefully monitored for any sign of TB reactivation.
- If the subject is diagnosed with **active TB**, the subject should not be randomized in the study and should not receive study drug. Subject will be considered as a **screening failure**.
- If the subject is diagnosed with **active TB** after being randomized, the subject should not receive any further study drug and follow the Week 52/Premature Discontinuation visit procedure (Section 2.1).
- If **TB (latent or active)** is diagnosed during the study, it is also necessary to report it as an AE in the source documents and eCRFs. In the case of a TB-related AE, a TB supplemental form that provides additional information will be completed by the investigator or designee.

Suspected Anaphylactic/Systemic Hypersensitivity Reaction Testing

Clinical criteria for diagnosing anaphylaxis are provided in Section 9.1. Blood tests to be conducted in the event of a suspected systemic hypersensitivity/ anaphylactic reaction:

- PK and ADA/NAb samples drawn in context of a suspected anaphylactic reaction are only collected if an anaphylactic reaction occurs while subject is at the study site.
 - A serum risankizumab, ADA, and NAb sample should be collected once within 24 hours.
- Serum tryptase: 15 minutes to 3 hours of symptom onset, and no later than 6 hours (as tryptase may remain elevated for 6 or more hours after the onset and therefore may still be informative if obtained after 3 hours).
- A follow-up tryptase level should be collected a minimum of 2 weeks after the recorded event or at the next study visit.
- Plasma histamine: 5 to 15 minutes of symptom onset, and no later than 1 hour.

Subjects will be closely monitored on site during study drug administration at all visits. A medical person qualified in the treatment of acute hypersensitivity reactions must be present during the injections. The duration of the post-dose safety surveillance is for 1 hour post-dose at all visits.

In the event that a suspected anaphylactic reaction occurs while the subject is not on site at the study clinic, please advise the treating facility to perform serum tryptase and histamine testing to help better understand and characterize the diagnosis and the Anaphylactic/Hypersensitivity Supplemental form will be completed.

COVID-19 Pandemic-Related Acceptable Protocol Modifications

If travel restrictions or other changes in local regulations in light of the COVID-19 pandemic prevent the subject from having blood drawn for laboratory testing at the study site, if possible, arrange for subjects to have laboratory work done at a local lab, hospital, or other facility. Local lab results should be obtained along with reference ranges and kept within the subjects' source documentation. Local lab results should be reviewed by the investigator as soon as possible.

If laboratory samples cannot be obtained, study drug administration may be continued provided the investigator has reviewed all prior laboratory results and confirms and discusses with the subject that there is no safety concern for the subject to continue use of the study drug in the absence of current labs. The subject should be scheduled for laboratory draws as soon as feasible within 7 days from the scheduled visit.

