Serum pregnancy test (for females of childbearing potential only)	✓							
TB test (QuantIFERON-TB Gold test [or IGRA equivalent] and/or local PPD skin test)	✓						✓	
Clinical chemistry, Hematology (including CBC)	✓	✓			✓		✓	
Urinalysis	✓							

Activity	Screening	Baseline	Week 4	Week 16	Week 28	Week 40	Week 52 / Premature Discontinuation	Follow-Up Call 20 Weeks after Last Dose
	Day -30 to Day -1	Day 1	Day 29	Day 113	Day 197	Day 281	Day 365	Day 421
Visit Window			± 3 Days		± 7 Days			
Rx TREATMENT								
Randomization/drug assignment in IRT		✓						
Study drug administration		✓	✓	✓	✓	✓		
In-clinic post-dose monitoring for hypersensitivity reactions		✓	✓	✓	✓	✓		

Optional Continuous Treatment Extension Study Activities Table

Activity	Week 52 of Main Study	Every 12 Weeks	CTE Withdrawal	Follow-Up Call 20 Weeks After Last Dose
		± 14 Day		
Informed consent	✓			
Adverse event assessment and concomitant medication	✓	✓	✓	✓
Pregnancy test	✓	✓	✓	
Risankizumab administration	✓	✓		

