10.3 Analysis of Laboratory Data

The clinical laboratory tests defined in the protocol operations manual (e.g., hematology, clinical chemistry, and urinalysis) will be summarized.

Each laboratory variable will be summarized for all time points (starting with Baseline) in Period A and B, with the number of non-missing observations, mean and standard deviation, median, minimum and maximum. Mean change from baseline to each applicable post-baseline visit will be summarized for selected laboratory variables, with the number of observations, baseline mean, and visit mean. The change from baseline mean, standard error, and 95% confidence interval will be presented for the mean change from baseline within each treatment group and difference between treatment groups.

Laboratory parameters will be tabulated using shift tables either by National Cancer Institute (NCI) Common Terminology Criteria (CTC) or categorized as low, normal, or high based on the normal ranges of the laboratory used for each sample. A shift table from baseline either to the worse value (based on NCI-CTC) during treatment or to minimum and maximum value (based on normal range), will be created in Period A and B. A similar shift table will be provided to summarize shifts from baseline to the final post-baseline value in Period A and B.

Laboratory abnormalities meeting NCI-CTC Grade 3 and 4 will be summarized in Period A (Safety Populations), B (Safety B Populations) and during the administration of risankizumab (ALL RZB Populations).

Laboratory abnormalities will be evaluated based on Potentially Clinically Significant (PCS) criteria ([Appendix C](#)), in Period A (Safety Populations), B (Safety B Populations) and during the administration of risankizumab (ALL RZB Populations). For each laboratory PCS criterion, the number and percentage of subjects who have a laboratory value meeting the criteria will be summarized. Listings will be provided to summarize subject-level laboratory data for subjects meeting PCS criteria.

In addition, the number and percentage of subjects meeting criteria for potential hepatotoxicity during the Treatment Period will be provided.

- ALT > 3 × ULN, > 5 × ULN, > 10 × ULN, > 20 × ULN
- AST > 3 × ULN, > 5 × ULN, > 10 × ULN, > 20 × ULN
- TBL > 1.5 × ULN, > 2 × ULN
- ALT and/or AST > 3 × ULN and TBL > 1.5 × ULN
- ALT and/or AST > 3 × ULN and TBL > 2 × ULN
- ALT > 3 × ULN and TBL > 1.5 × ULN
- ALT > 3 × ULN and TBL > 2 × ULN
- Alkaline phosphatase > 1.5 × ULN

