Appendix C. Potentially Clinically Significant Criteria for Safety Endpoints

The criteria for Potentially Clinically Significant (PCS) laboratory findings are described in Table C-1 and Table C-2, and the PCS criteria for vital sign findings are described in Table C-3.

Table C-1. Criteria for Potentially Clinically Significant Hematology Values

Hematology Variables	Units	Definition of Potentially Clinically Significant Current (Version 4.03) NCI CTCAE Grade 3 or Greater	
		Very Low	Very High
Hemoglobin	g/dL	< 8.0	
Platelets count	10 ⁹ /L	< 50.0	
WBC count	10 ⁹ /L	< 2.0	
Neutrophils	10 ⁹ /L	< 1.0	
Lymphocytes	10 ⁹ /L	< 0.5	

Note: A post baseline value must be more extreme than the baseline value to be considered a potentially clinically significant finding.

Table C-2. Criteria for Potentially Clinically Significant Chemistry Values

Chemistry Variables	Units	Definition of Potentially Clinically Significant Current (Version 4.03) NCI CTCAE Grade 3 or Greater	
		Very Low	Very High
TBL	mcmol/L		$> 3.0 \times \text{ULN}$
ALP	U/L		$> 5.0 \times \text{ULN}$
SGOT/AST	U/L		$> 5.0 \times \text{ULN}$
SGPT/ALT	U/L		$> 5.0 \times \text{ULN}$
Albumin	g/L	< 20	
Glucose	mmol/L	< 2.2	> 13.9
Triglycerides	mmol/L		> 5.7
Creatinine	mcmol/L		$> 3.0 \times \text{ULN} (> 3.0 \times \text{BL})$
Sodium	mmol/L	< 130	> 155
Potassium	mmol/L	< 3.0	> 6.0
Calcium	mmol/L	< 1.75	> 3.1
CPK	U/L		$> 5.0 \times \text{ULN}$
Total Cholesterol	mmol/L		> 10.34
GGT			$> 5.0 \times \text{ULN}$

Note: A post baseline value must be more extreme than the baseline value to be considered a potentially clinically significant finding.

Table C-3. Criteria for Potentially Clinically Significant Vital Sign Values

Vital Signs Variables	Criterion	Definition of Potentially Clinically Significant
Systolic Blood Pressure (mmHg)	Low	Value ≤ 90 mmHg and decrease ≥ 20 mmHg from Baseline
	High	Value ≥ 160 mmHg and increase ≥ 20 mmHg from Baseline
Diastolic Blood Pressure (mmHg)	Low	Value ≤ 50 mmHg and decrease ≥ 10 mmHg from Baseline
	High	Value ≥ 100 mmHg and increase ≥ 10 mmHg from Baseline

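### Glucose is fasting at Baseline but need not be at Weeks 28 and 52, so within-group glucose change and shift tables can show a meal effect as a rise on risankizumab

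*Protocol*

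**What the plan says.** **Collection.** Operations Manual Section 3.12 states: "The blood samples for serum chemistry tests will be collected following a minimum 8-hour fast for the Baseline/Day 1 visit". It names glucose, total cholesterol, LDL-C, HDL-C and triglycerides. If a subject has not fasted for that visit, "the non-fasting status will be recorded in study source documentation and lab requisition". For every other visit, "Blood samples at other visits can be drawn without prior fast". The laboratory baseline is "defined as the last measurement prior to the initial dose of study drug", which is normally the fasting Day 1 sample.

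**Schedule.** In Protocol Appendix D, chemistry is drawn at Screening, Baseline, Week 28 and Week 52/Premature Discontinuation. None is scheduled at Weeks 4, 16 or 40.

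**Lipids.** In the laboratory table of Section 3.12, the four lipids carry footnote b, which begins "Performed at Baseline/Day 1 visit (following a minimum 8-hour fast". Glucose carries no footnote.

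**Analysis.** SAP Section 10.3 summarises every laboratory variable at all time points and plans shift tables from baseline to the worst (or minimum and maximum) value and to the final value. It adds: "Mean change from baseline to each applicable post-baseline visit will be summarized for selected laboratory variables". The selection is not named. Change is reported within each treatment group and as a difference between groups, with 95% CIs. SAP Table C-2 sets high limits for glucose (13.9 mmol/L), triglycerides (5.7 mmol/L) and total cholesterol (10.34 mmol/L), with the condition that "A post baseline value must be more extreme than the baseline value to be considered a potentially clinically significant finding". The SAP does not mention fasting.

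**The concern.** For glucose, a baseline-referenced summary compares a fasting value with a later value whose fasting status is unknown. If some later samples follow a meal, average glucose rises for a reason unrelated to treatment.

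In a placebo-controlled period, the control arm would show the same rise and the contrast would remove it. Here both scheduled post-baseline chemistry visits fall in Period B, when all subjects receive open-label risankizumab. A reader of the within-group tables, or of the all-risankizumab summaries, could not tell a meal effect from a metabolic effect of the drug.

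What is at stake is the interpretation of secondary safety tables. No efficacy endpoint is involved.

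**Working it through.** The documents give no figure for a fasting effect or for glucose variability, so there is no plan figure to reproduce. The meal shifts, SDs, means and non-fasting shares below are assumptions. Only the group size (50 per arm in each study), the visit schedule and the Table C-2 limits come from the documents.

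**1. Schedule count.** Scheduled post-baseline chemistry visits: Period A, 0 (none at Weeks 4 or 16); Period B, 2 (Weeks 28 and 52). A Premature Discontinuation visit or an unscheduled draw could add an isolated Period A value.

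**2. Bias formulas.**
- Within-group change: bias = (share of later samples non-fasting) × (mean meal shift).
- Between-group difference: bias = (difference in non-fasting share between groups) × (mean meal shift). This is 0 when the shares are equal. With a 10-point imbalance and a shift of 0.5 mmol/L it is 0.10 × 0.5 = 0.05 mmol/L.

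**3. Chance that the CI for mean change lies above zero with no drug effect.** Take an SD of change of 1.2 mmol/L and n = 50, so SE = 1.2/√50 = 0.170. The probability is 1 − Φ(1.96 − bias/SE); with no bias it is 2.5%.

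| Meal shift (mmol/L) | All later samples non-fasting: bias, probability | Half non-fasting: bias, probability |
|---|---|---|
| 0.3 | 0.30, 42% | 0.15, 14% |
| 0.5 | 0.50, 84% | 0.25, 31% |
| 1.0 | 1.00, about 100% | 0.50, 84% |

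The half column keeps the SD at 1.2. With an SD of 1.5 instead and all later samples non-fasting, SE = 0.212, and shifts of 0.3 and 0.5 give about 29% and 65%.

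**4. Threshold counts.** These use a lognormal distribution with all later samples non-fasting.

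| Analyte and limit | Assumed fasting mean (SD), mmol/L | Assumed shift | Above limit, fasting | Above limit, non-fasting |
|---|---|---|---|---|
| Glucose > 13.9 | 5.5 (1.5) | 0.5 to 2 | 0.02% | 0.02% to 0.07% |
| Glucose > 13.9 | 6.0 (2.5) | 0.5 to 2 | 1.1% | 1.3% to 2.5% |
| Triglycerides > 5.7 | 1.6 (1.0) | 0.2 to 1 | 0.6% | 0.7% to 1.1% |
| Triglycerides > 5.7 | 2.0 (1.3) | 0.2 to 1 | 2.0% | 2.2% to 4.0% |

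The largest increase is 4.0% − 2.0%, or about 2 extra subjects per 100, and it is for triglycerides. For glucose it is 2.5% − 1.1%, or about 1.4 per 100. Total cholesterol was not modelled.

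**5. Lipids.** Footnote b can mean that lipids are measured only at Baseline, or that they are fasting only at Baseline. Footnotes d and h in the same table use the word only where they restrict a test, and footnote b does not, so the text does not settle it. On the first reading, the triglyceride and cholesterol rows of Table C-2 have no scheduled post-baseline data. On the second, lipids share the glucose problem.

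**The case against.** A reader might infer that the planned glucose and lipid analyses are biased throughout, or empty. The documents do not support that, for these reasons:

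- **Between-group difference.** Both randomised groups follow the same visit rule, so the difference has no expected bias from fasting. This stands. In Period B, however, that contrast is continued risankizumab against placebo switched to risankizumab, so it does not isolate a drug effect from a meal effect either.
- **Mean change.** It is planned only for an unnamed selection of variables, and glucose may not be among them. This stands. The shift tables carry no such restriction and are the firmer target.
- **Size.** Non-fasting samples are allowed, not required, so the 42%, 84% and 100% figures are an upper case. The laboratory CIs are descriptive and trigger no decision. Both points stand.
- **Thresholds.** The Table C-2 limits are Grade 3 or greater, and few subjects would cross them because of a meal. This stands.
- **Empty tables.** This could apply only to lipids, and only on one reading of footnote b. Glucose has Week 28 and Week 52 data.
- **Open-label samples only.** This is true of the scheduled visits at Weeks 28 and 52, not of every possible draw, as step 1 of the working notes.

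Restricting everything to fasting samples would also be a poor remedy. It could discard most later values, keep a self-selected subset, and remove genuine severe hyperglycaemia from the safety counts.

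None of this removes the core mismatch: a fasting baseline, later samples of unrecorded status, and within-group summaries with no fasting rule.

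**Conclusion.** The point holds for within-group glucose summaries in Period B and in the all-risankizumab populations: shift tables in any case, and mean change if glucose is selected. Under the stated assumptions, the meal effect alone could put the mean-change CI above zero in anything from about 14% of trials (0.3 mmol/L shift, half non-fasting) to nearly all (1.0 mmol/L shift, all non-fasting). The true figure depends on the actual meal shift, the SD of change and the non-fasting share, none of which the documents give.

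The Table C-2 counts are little affected, and the lipid question is an ambiguity to settle. This is a minor improvement to secondary safety reporting.

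**What to change.** 1. In Operations Manual Section 3.12, record fasting status on the laboratory requisition at Weeks 28 and 52.
2. In SAP Section 10.3, present glucose change and shift summaries by fasting status or on like-for-like samples. One option is an additional comparison against the Screening sample, which needs no fast either. Label values of unknown status as mixed. State whether glucose is among the variables selected for mean change.
3. Keep all samples in the Table C-2 threshold counts and flag them by fasting status.
4. State what footnote b means. If lipids are measured only at Baseline, drop the triglyceride and total cholesterol rows from Table C-2. If not, apply the same rule to lipids as to glucose.

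The cost is one requisition field, some SAP wording, and fewer values in each like-for-like summary. Visits, dosing, randomisation, and the primary and ranked endpoints do not change.
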